12.3 Device performance and deficiency

Detailed instructions and training on the application of MAR-CUTIS and Dermabond Advanced will be provided to each investigational center.

The performance of the IMD in each subject will be recorded in the e-CRF. Additionally, the device deficiency (due to e.g. malfunction or user error) and the early glue detachment of removal (as well as the reasons and timing) will be assessed. All data will be presented in subject listings.

For device performance, the following variables will be summarized descriptively: overall performance of the IMD, whether any AE/SAE occurred during application or since the last visit, and if the correction of adhesive was performed (and if done within the stipulated time).

For device deficiency, the following variables will be summarized descriptively: any deficiency occurred with the IMD during the application or at subsequent visits, type of deficiency, whether the deficiency lead to a serious deterioration of the subject's health, description of deficiency, and location where the incident occurred.

12.4 Premature and/or unintentional detachment of glue

The premature and/or unintentional detachment of the glue will be recorded in the e-CRF. All data will be listed. The following variables will be summarized descriptively: whether the glue was prematurely or unintentionally detached and the surrounding condition at time of detachment.

13 EFFICACY ANALYSES

13.1 Primary endpoint

The primary efficacy endpoint is the total dehiscence rate of target incision/laceration assessed until the Day 10 visit. For this analysis, all evaluations of dehiscence until Day 10 (at Day 1, Day 10 or other unscheduled visits before Day 10) will be included in the analysis.

13.1.1 Main analysis

The primary efficacy analysis will be performed on the FAS population. All subjects should be treated under equal conditions at all centers and no center-specific variance effects are considered.

During this trial, it is expected that a subject will have only one incision/laceration treated with the IMD (= target wound). In case the subject has more than one incision/laceration, the target wound will be the one with the greatest length (i.e., the longest) that meets the study entry criteria. If the

length of 2 or more wounds is equal, the investigator can choose either of them to be the target wound. Dehiscence will be assessed only for the target wound; for the analysis of the primary efficacy endpoint, only the treated target wound can and will be analyzed.

In the context of the primary endpoint, dehiscence will be defined as “Yes” if the treated wound shows dehiscence until Day 10, or “No” if the wound remains closed. Thus, if the wound is assessed as showing dehiscence at Day 1 but showing no dehiscence at Day 10, dehiscence will be evaluated as “Yes” in the main analysis.

To minimize any possible user bias in the dehiscence rates, investigational centers will provide adequate training to all device users in cooperation with the sponsor. The evaluation of dehiscence, as well as the dehiscence classification and classification according to their grade will be recorded in the e-CRF.

The primary null and alternative hypotheses to be tested in this trial is that treatment with MAR-CUTIS is noninferior to treatment with Dermabond at the margin of 8%, i.e.

$$H_0: p_M - p_D \geq 0.08 \text{ versus } H_1: p_M - p_D < 0.08$$

where p_M is the dehiscence rate of subjects treated with MAR-CUTIS, and p_D is the dehiscence rate of subjects treated with Dermabond. Since the dehiscence rates for both treatments are influenced by several factors, the effect of these will be considered and estimated with a statistical model.

Maximum-Likelihood estimates (MLEs) will be obtained fitting a logistic regression model to the dehiscence rates using the skin type (types I to III ; types IV to VI), age group (pediatric with age between 2-21 years; adult with age ≥ 22 years), type of wound (incision; laceration) and treatment (MAR-CUTIS; Dermabond Advanced) as explanatory variables. The model will be estimated in SAS using proc logistic and the LSMEANS statement with the option OBSMARGINS, in order to specify a potentially different weighting scheme for the computation of the MLE coefficients across classification effects. The weighting scheme will be the same as in the analysis data set (default use of option OBSMARGIN).

The MLEs of the treatment effect obtained with the logistic regression will provide the logit estimates for both treatments, defined as:

$$\text{logit}_M = \log(p_M / (1 - p_M))$$

$$\text{logit}_D = \log(p_D / (1 - p_D))$$

for MAR-CUTIS and Dermabond, respectively. Thus, by transforming the MLEs to the linear scale, estimates of the Odds are given with:

$$\text{Odds}_M = p_M / (1 - p_M)$$

$$\text{Odds}_D = p_D / (1 - p_D)$$

for p_M and p_D . Therefore, estimated event probabilities for p_M and p_D , denoted by p_M^* and p_D^* , can be obtained with:

$$p_M^* = \text{Odds}_M / (\text{Odds}_M + 1)$$

$$p_D^* = \text{Odds}_D / (\text{Odds}_D + 1).$$

After the event probabilities defined above are estimated by fitting the logistic regression model with the event of interest given by Dehiscence occurrence (i.e., if Dehiscence='Yes' then event=1), the inverse probabilities denoted by q_M^* and q_D^* can be obtained as:

$$q_M^* = 1 - p_M^*$$

$$q_D^* = 1 - p_D^*$$

for MAR-CUTIS and Dermabond, respectively. Using these four estimated probabilities, it is possible to construct a contingency table of the form:

	Dehiscence = No (0)	Dehiscence = Yes (1)
Treatment = Dermabond	$N_D \times q_D^*$	$N_D \times p_D^*$
Treatment = MAR-CUTIS	$N_M \times q_M^*$	$N_M \times p_M^*$

where N_M is the number of subjects treated with MAR-CUTIS, and N_D is the number of subjects treated with Dermabond.

Based on this contingency table, a comparison of the response rates of both treatments using the method of Farrington-Manning (FM; [Farrington and Manning, 1990](#)) will be performed. The FM estimate for the standard error, the p-value of the FM test regarding non-inferiority, and the two-sided 90% confidence interval (CI) for the difference in dehiscence rates will be obtained and reported.

Non-inferiority of MAR-CUTIS compared with Dermabond Advanced will be declared if the p-value of the FM test is significant at the level $\alpha=0.05$ and the upper limit of the two-sided 90% CI is below the non-inferiority margin of 8%.

Subjects with problems of wound closure are expected to attend the Day 10 visit to see the investigator and assess the wound status. If the subject is unable to attend the Day 10 visit on-site, he/she will be contacted by phone to obtain the information to assess wound closure. For the primary endpoint main analysis on the FAS, any missing data will be imputed as follows:

- Subjects with a provided reason for not attending Day 10 visit related to problems with the wound closure will be counted as failure, i.e. the subject experiences a dehiscence (Dehiscence="Yes")
- Subjects with a dehiscence experienced and recorded before the Day 10 visit (Day 1 or unscheduled visit) will be counted as failure, i.e. the subject experiences a dehiscence (Dehiscence="Yes")
- All other subjects (e.g., lost to follow-up with no dehiscence before) will be counted as a success, i.e. the subject experiences no dehiscence up to Day 10 (Dehiscence="No"), since it is expected that subjects with problems of wound closure would attend the Day 10 visit to see the investigator and assess the wound status, and given the very low expected rate of dehiscence

In any case, all efforts will be made to contact subjects not attending Day 10 visit to gain information about the reason for nonattendance and about potential dehiscence. Descriptive statistics of the evaluation, grading and classification of dehiscence as recorded in the e-CRF and following the imputation rule will be presented for overall and the sub-groups described in Section 8.2.1.

Convergence of model fit

Following [Mallinckrodt et al. \(2008\)](#) we prespecify a fixed sequence of measures to further increase stability of the model to ensure convergence of the primary analysis model. The following prespecified fixed sequence will be applied until a converging model is found:

1. Fit a logistic regression model to the dehiscence rates using the treatment, age group, and skin type and type of wound as explanatory variables
2. Fit a logistic regression model to the dehiscence rates using the treatment, age group, and type of wound as explanatory variables.
3. Fit a logistic regression model to the dehiscence rates using the treatment and type of wound as explanatory variables.
4. Fit a logistic regression model to the dehiscence rates using treatment as explanatory variable

The first converging model in this sequence will be the primary analysis model. This testing sequence is defined based on the expected clinical relevance of the respective explanatory variables. Moreover, this approach is consistent with the dynamic allocation algorithm implemented for the randomization (see [Section 5.3](#) for more details).

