##### 10.1.3.1.2 Main Analysis

During this trial, it is expected that a subject will have only one incision/laceration treated with the IMD (=target wound). In case the subject has more than one incision/laceration, the target wound will be the one with the greatest length (ie, the longest) that meets the study entry criteria. If the length of 2 or more wounds is equal, the investigator can choose either of them to be the target wound. Dehiscence will be assessed only for the target wound; for the analysis of the primary efficacy endpoint, only the treated target wound can and will be analyzed.

To minimize any possible user bias in the dehiscence rates, sites will provide adequate training to all device users in cooperation with the sponsor.

Missing data will be handled as described in Section 10.1.5.

The primary null and alternative hypotheses to be tested in this trial is that treatment with MAR-CUTIS is noninferior to treatment with Dermabond at the margin of 8%, ie,

$$H_0: p_M - p_D \geq 0.08 \text{ versus } H_1: p_M - p_D < 0.08$$

where  $p_M$  is the dehiscence rate of subjects treated with MAR-CUTIS, and  $p_D$  is the dehiscence rate of subjects treated with Dermabond. Since the dehiscence rates for both treatments are influenced by several factors, the effect of these will be considered and estimated with a statistical model.

---

Maximum-Likelihood estimates will be obtained fitting a logistic regression model to the dehiscence rates using the 3 randomization factors skin type (types I to III/types IV to VI), age group (2-21/ $\geq 22$  years) and type of wound (incision/laceration), as well as treatment (MAR-CUTIS/Dermabond Advanced) as explanatory variables.

The method of Farrington-Manning (FM; Farrington and Manning, 1990) will be applied to determine the variance estimator.

Noninferiority will be declared if the upper limit of the 90% confidence interval (computed using the FM method) of the risk difference (computed from Maximum-Likelihood estimates after fitting a logistic regression) MAR-CUTIS:Dermabond is less than 8% in the FAS.

If the logistic regression model as describe above does not converge due to a low number of subjects in one or more of the stratification factors, a back-up strategy for the analysis will be provided in the SAP.

The following sensitivity analyses for primary efficacy will be performed:

- 1) The primary efficacy analysis as described above will be repeated using the PPS.

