13.1.2 Sensitivity analysis

The following sensitivity analyses for primary efficacy will be performed:

- 1) The primary efficacy analysis as described above will be repeated using the PPS.
- 2) An analysis will be performed by repeating the logistic regression model described in the primary efficacy main analysis, albeit considering the length of the incision/laceration in the logistic regression model instead of the type of wound. This analysis will be performed using the FAS.
- 3) The primary efficacy analysis will be repeated, albeit by considering subjects with missing data for the primary efficacy analysis as experiencing “Yes” dehiscence (i.e., the wound did not remain closed). This analysis will be performed using the FAS. Descriptive statistics of dehiscence assessment following this second imputation rule will be added to the dehiscence descriptive statistics summary described in [Section 13.1.1](#).
- 4) An additional sensitivity analysis will be performed using a Cochran-Mantel-Haenszel (CMH; [Cochran, 1954](#); [Mantel and Haenszel, 1959](#)) test. The dehiscence rates MAR-CUTIS:Dermabond will be analyzed with the CMH test, stratified by skin type (types I to III ; types IV to VI), age group (pediatric with age between 2-21 years; adult with age ≥ 22

years), type of wound (incision; laceration) and treatment (MAR-CUTIS; Dermabond Advanced). This analysis will be performed using the FAS.

- 5) A final sensitivity analysis will be performed by repeating the logistic regression model described in the primary efficacy main analysis, albeit introducing additionally the effect of the center where the subject was treated (given by the center ID) in the logistic regression model. This analysis will be performed using the FAS, and will only be considered if the logistic regression model converges.

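### The primary analysis averages logits, not risks, so at low dehiscence rates it understates a MAR-CUTIS excess against the 8% margin whenever a covariate with an effect stays in the model

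*SAP*

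**What the plan says.** SAP 13.1.1 sets H0 as p_M − p_D ≥ 0.08, "where p_M is the dehiscence rate of subjects treated with MAR-CUTIS" and p_D is its Dermabond counterpart. Protocol 10.1.3.1.2 declares noninferiority if the upper 90% confidence limit of the "risk difference (computed from Maximum-Likelihood estimates after fitting a logistic regression) MAR-CUTIS:Dermabond is less than 8% in the FAS".

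The model is a logistic regression on treatment, skin type, age group and wound type. On estimation the SAP says: "The model will be estimated in SAS using proc logistic and the LSMEANS statement with the option OBSMARGINS", with weights taken from the analysis data set. The resulting single logit per arm is turned into odds and then into p*. The SAP continues: "Using these four estimated probabilities, it is possible to construct a contingency table of the form". Its cells are N × p* and N × (1 − p*), and the FM standard error, p-value and interval are computed from them.

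On convergence: "The following prespecified fixed sequence will be applied until a converging model is found". Skin type is dropped first, then age group, then wound type, which leaves treatment alone at step 4. "The first converging model in this sequence will be the primary analysis model". The protocol foresees a back-up strategy if the model "does not converge due to a low number of subjects in one or more of the stratification factors". Neither document mentions separation.

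**The concern.** Adjusting with a logistic model is intended and is not the problem. The problem is the scale on which the covariates are averaged. Observed-margin least-squares means average the linear predictor, and inverting that average gives the risk of a notional subject with average covariates. It does not give the average risk of the subjects treated.

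The second-order approximation is: average risk − p* ≈ ½ · Var(logit) · p(1 − p)(1 − 2p), where Var(logit) is the spread of the covariate part. This is positive below 50% and rises with p up to (3 − √3)/6 = 21.1%. At low rates the arm with more dehiscence is therefore shrunk more, and a positive difference moves towards zero. If MAR-CUTIS is worse, the shift favours noninferiority, and this is the situation in which type I error is set.

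The planned sensitivity analyses do not repair it. Item 2 of SAP 13.1.2 reads "An analysis will be performed by repeating the logistic regression model described in the primary efficacy main analysis", with wound length in place of wound type. Items 1, 3 and 5 also reuse the estimator. Item 4, a Cochran-Mantel-Haenszel test, names no 8% margin.

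A second gap sits beside this one. The sequence depends on convergence, but the SAP does not say whether a separated fit (no events in a factor level) counts as converging.

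**Working it through.** **Inputs.** From SAP 5.2: 126 vs 63 subjects; 3.05% vs 0.85%; margin 8%; one-sided α 0.05; lacerations 15% of subjects at 0.5% vs 0%; incisions 85% at 3.5% vs 1%. From Protocol 7.2.1: about 40 subjects with lacerations, 40 with skin types IV–VI and 30 aged 2–21.

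**1. The plan's own figures reproduce.** Exact binomial enumeration of the FM score test gives 85.8% power (stated: 85%). The planning rates are averaged risks: 0.15 × 0.5% + 0.85 × 3.5% = 3.05%, and 0.15 × 0% + 0.85 × 1% = 0.85%.

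**2. The SAP estimator does not return those rates.** The additive logistic model (treatment, wound type) was fitted to the expected planning cells:

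| Lacerations | SAP method | Averaged risks |
|---|---|---|
| 15% | 2.58% vs 0.72%, difference 1.87, upper limit 6.06% | 3.05% vs 0.85%, difference 2.20, upper limit 6.44% |
| 40/189 | difference 1.66, upper limit 5.81% | difference 2.08, upper limit 6.29% |

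The difference is 15% to 20% too small.

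**3. A true 8-point excess, wound type in the model, large sample.** The odds ratio (OR) from the MAR-CUTIS rates is (0.005/0.995)/(0.035/0.965) = 0.139, with log −1.977. Using it in both arms is an assumption, because the plan gives 0% for Dermabond lacerations. Take Dermabond 0.85%, MAR-CUTIS 8.85% and 15% lacerations:

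- Dermabond: incisions 0.98%, lacerations 0.14%. Averaged logit = −4.620 + 0.15 × (−1.977) = −4.916, so p_D* = 0.73%.
- MAR-CUTIS: incisions 10.14%, lacerations 1.54%. Averaged logit = −2.182 + 0.15 × (−1.977) = −2.478, so p_M* = 7.74%.
- Estimated difference: 7.74 − 0.73 = 7.01 points.

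| Dermabond rate | 15% lacerations: estimate / effective margin | 40/189: estimate / effective margin |
|---|---|---|
| 0.85% | 7.01 / 9.10 | 6.68 / 9.52 |
| 2.5% | 7.08 / 9.02 | 6.77 / 9.41 |
| 5% | 7.17 / 8.90 | 6.90 / 9.24 |

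The effective margin is the true excess that the method estimates as 8 points. The pull reverses at Dermabond rates of 25.7% (15% lacerations) and 24.9% (40/189). If MAR-CUTIS is 2 points better, −2.0 is estimated as −1.6 to −1.7 (Dermabond 2.5–5%), which works against noninferiority.

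**4. Type I error over the whole sequence.** All four models were simulated in SAP order at a true 8-point excess, with 20,000 trials per setting (Monte Carlo SE 0.15 points at 5%, 0.20 at 9%). Settings: 28 or 40 lacerations, factors independent and each split 2:1, Dermabond 0.85/2.5/5%. Separated fits were sent down the sequence, and observed proportions were used if step 4 was also separated. Age and skin ORs (0.5–2) are assumptions.

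| Covariate effects | SAP method | Averaged risks |
|---|---|---|
| Wound OR 0.139, age and skin ORs 0.5–2 | 5.1–6.3% | 4.6–5.4% |
| All ORs 1 | 5.8–6.4% | 4.9–5.6% |
| All ORs 2 | 6.8–9.0% | 4.7–5.1% |
| Full grid, wound OR 0.139–2 | 5.1–9.0% | 4.6–5.6% |

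The gap is 0.1–1.3 points in the first row and 0.1–4.2 over the grid. A covariate was retained in 12–96% of these trials, and virtually every changed decision went towards noninferiority. A separately coded simulation (4,000 trials per setting) gave 5.0–6.4% vs 4.7–5.7% at wound OR 0.139, and 7.2–7.8% vs 4.5–5.2% with all ORs 2.

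**5. A case that can be refitted.** These are constructed data, chosen because the decision changes, with treatment and wound type in the model. There are 19 MAR-CUTIS and 10 Dermabond lacerations. Events are 4 incision + 4 laceration on MAR-CUTIS and 2 + 0 on Dermabond.

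| Method | Difference | Upper limit | p |
|---|---|---|---|
| SAP | 2.89 | 7.83% (noninferior) | 0.044 |
| Averaged risks | 3.24 | 8.39% (not shown) | 0.064 |
| Observed (8/126 vs 2/63) | 3.17 | 8.33% (not shown) | 0.062 |

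**6. Separation is the expected case at the planning rates.** The chance of no laceration event is 0.995^18.9 = 91% (126 × 0.15 = 18.9 MAR-CUTIS lacerations) or 0.995^26.7 = 87% (126 × 40/189 = 26.7). The chance of no Dermabond event is 0.9915^63 = 58%. Step 1 was separated in 96–99% of trials simulated at the planning rates.

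**The case against.** The strongest reply concerns size. The effective margin of 8.9–9.5 points assumes that wound type is always retained, whereas the SAP has a fallback. At the only covariate effect that can be taken from the documents, the type I excess over the full sequence is 0.1–1.3 points, and near the planned Dermabond rate it can lie within simulation noise. This stands. The 9.0% figure needs all three ORs equal to 2. No document gives an age or skin-type effect, and a wound OR of 2 contradicts the planning assumption that lacerations dehisce less. It is the top of an assumed range, not a forecast.

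It is also fair that a true covariate effect is not strictly needed. With all ORs 1 there is still some inflation, because chance coefficients in a retained model have the same effect. This widens the problem rather than removing it.

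On separation, a separated fit has no finite maximum-likelihood estimate, so the natural reading sends it down the sequence. The figures above use that reading. If such fits were accepted, which the SAP neither requires nor forbids, type I error would depend on where the software stops. Under an assumed stop after 8 Newton steps it was 7–76%, against 4.5–5.5% with averaged risks on the same fits. The conclusion does not rest on this.

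Finally, SAP 13.1.1 also plans descriptive dehiscence rates, so a reader would see the observed proportions. They do not enter the decision rule.

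**Conclusion.** The concern holds. The SAP estimates a quantity different from the one in its hypothesis, in the protocol's decision rule and in its own sample-size calculation. At low rates with MAR-CUTIS worse, the discrepancy favours the sponsor's claim.

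The document-based excess in type I error is modest (0.1–1.3 points, assuming the MAR-CUTIS wound OR in both arms). It grows to 4.2 points under the strongest assumed covariate effects. It is absent in the treatment-only model and reverses at Dermabond rates above about 25%. Direction and mechanism are certain. The size depends on covariate effects that the plan mostly does not state. This should be fixed before the analysis. The missing separation rule is secondary.

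**What to change.** In SAP 13.1.1, replace the least-squares-means back-transformation by: for each Full Analysis Set subject, predict the dehiscence probability with treatment set to MAR-CUTIS and again with treatment set to Dermabond Advanced; p_M* and p_D* are the averages of these predictions over the Full Analysis Set. Model, FM table, test and margin stay. In the simulations the unchanged FM variance with averaged risks kept type I error at 4.6–5.6%.

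In the convergence paragraph add: complete or quasi-complete separation counts as non-convergence; if the treatment-only model is also separated because an arm has no events, the observed proportions enter the FM table. The last clause is a tidy-up with almost no numerical effect.

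The cost is SAP wording and a few lines of code. Protocol 10.1.3.1.2 is still met, since averaged predictions are also a risk difference from maximum-likelihood estimates after logistic regression. When a covariate is retained and MAR-CUTIS is worse, the estimate becomes slightly less favourable to it. Power at the planning rates is 85.7–88.9% under both methods, at most about 0.2 points apart, because a covariate is retained in only 4–5% of those trials. One consequence should be accepted openly: with no Dermabond events every model is separated, so the stratification factors drop out of the primary analysis in those trials.

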### Study Centers:

Up to 22 study centers located in the European Union

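### The primary-model sequence in SAP 13.1.1 does not say whether a separated logistic fit counts as converging, and it stops at a model that a zero-event arm also separates

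*SAP*

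**What the plan says.** SAP 13.1.1 estimates the two dehiscence rates from a logistic model with treatment, age group, skin type and wound type: "The model will be estimated in SAS using proc logistic and the LSMEANS statement with the option OBSMARGINS". The averaged logits are back-transformed, multiplied by the arm sizes to give a fitted 2x2 table, and FM is applied to that table. The decision rests on it: "Non-inferiority of MAR-CUTIS compared with Dermabond Advanced will be declared if the p-value of the FM test is significant" at 0.05 and the upper 90% limit is below 8%.

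For sparse data, "we prespecify a fixed sequence of measures to further increase stability of the model to ensure convergence of the primary analysis model". Skin type is dropped first, then age group, then wound type. Step 4 is "Fit a logistic regression model to the dehiscence rates using treatment as explanatory variable", and "The first converging model in this sequence will be the primary analysis model".

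Protocol 10.1.3.1.2 leaves the back-up strategy to the SAP, so the rule could stand nowhere else. The CMH test in SAP 13.1.2 is a sensitivity analysis and not a fallback. Sensitivity analysis 5, which adds center, "will only be considered if the logistic regression model converges".

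**The concern.** Neither document mentions separation. With few events it can arise in two ways, with different consequences.

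- **A covariate level has no events**, most often lacerations. Dropping that covariate cures it.
- **A treatment arm has no events.** Treatment is in all four models, so no step cures it.

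**Reading (a): a separated fit does not count as converging.** A zero-event arm exhausts the sequence and no primary model is named. The replacement test would be chosen after the data are seen, in an open-label trial.

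**Reading (b): a separated fit counts.** The sequence can stop at a model whose wound-type coefficient is diverging. Because the rates are averaged on the logit scale over the observed wound-type mix, that coefficient pulls both fitted rates toward zero, and their difference with them. The fitted table then shows a difference the patients did not have. The SAP does tabulate what was observed ("Descriptive statistics of the evaluation, grading and classification of dehiscence as recorded in the e-CRF"), but the declaration uses only the fitted table.

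**Working it through.** **Inputs.** Rates 3.05% and 0.85%, 126 vs 63 subjects, margin 8%, one-sided 0.05 (Protocol 10.2, SAP 5.2). Lacerations: 15% of subjects at 0.5% (MAR-CUTIS) and 0% (Dermabond); incisions 3.5% and 1%. Laceration stratum: 15% of 189 is about 28 (19 vs 9 at 2:1), whereas Protocol 7.2.1 plans about 40 (27 vs 13); both were run.

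**1. The plan's own power.** 0.15 x 0.5% + 0.85 x 3.5% = 3.05% and 0.85 x 1% = 0.85%. Summing binomial probabilities over all tables in which FM on counts rejects gives 85.8%, which agrees with the stated 85%. The exact size of the same test at 8.85% vs 0.85% is 5.1%.

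**2. Reading (a).**
- P(0/63) = 0.9915^63 = 0.584. P(0/126) = 0.9695^126 = 0.020.
- Either arm empty: 0.584 + 0.020 - 0.584 x 0.020 = 0.592. Simulation by wound type gives 59% with 28 lacerations and 62% with 40.
- If the Dermabond rate is 2%, P(0/63) is 28%; at 2.5% (the figure Protocol section 5 gives for other adhesives) 20%; at 5%, 4%.
- The choice of replacement can matter. At 5/126 vs 0/63 the restricted estimates are 0.08 and 0, so SE = sqrt(0.08 x 0.92/126) = 0.0242, z = (0.0397 - 0.08)/0.0242 = -1.668 and p = 0.048. An exact unconditional version gives 0.057. P(5/126 and 0/63) = 0.152 x 0.584 = 0.089.

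**3. Reading (b), how often.** P(no laceration event) = 0.995^19 = 0.91 with 28 lacerations and 0.995^27 = 0.87 with 40.

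**4. Reading (b), mechanism.** Take 28 lacerations, none dehisced, and 11/126 vs 1/63, in a model with treatment and wound type. Incision rates are 11/107 and 1/54. With laceration coefficient b, each arm's averaged logit is its incision logit plus b x 28/189. At b = -10:
- MAR-CUTIS: ln(11/96) - 1.481 = -3.648, a rate of 2.5% (observed 8.7%).
- Dermabond: ln(1/53) - 1.481 = -5.452, a rate of 0.4% (observed 1.6%).
- The FM upper 90% limit is 6.2% (pass), against 12.1% on counts (fail).

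The coefficient reached depends on the stopping tolerance. For 14/126 vs 2/63 under the same conditions, FM p = 0.058 / 0.007 / 0.002 at tolerances 1e-4 / 1e-6 / 1e-8. On counts p = 0.49, with an upper limit of 13.8%.

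**5. Reading (b), type I error** at 8.85% vs 0.85% overall. There were 4000 runs per setting. Assumptions: 30 subjects aged 2-21 and 40 with skin types IV-VI, neither factor with an effect; Dermabond lacerations at 0%; Newton fit with at most 25 iterations. The incision rate is set to keep 8.85% overall, e.g. (126 x 8.85% - 19 x 0.5%)/107 = 10.3%.

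| Lacerations | MAR-CUTIS laceration rate | Tolerance 1e-4 | Tolerance 1e-8 |
|---|---|---|---|
| 28 | 0.5% | 71% | 93% |
| 28 | 2% | 60% | 74% |
| 28 | 4% | 48% | 57% |
| 28 | 8.85% | 33% | 35% |
| 40 | 0.5% | 88% | 89% |
| 40 | 8.85% | 29% | 30% |

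FM on observed counts in the same runs: 4.6-5.2%. With Dermabond lacerations also at 0.85% and MAR-CUTIS at 8.85% throughout, the modelled test gives 27-33%. Separation is the cause: with 28 lacerations at 0.5%, noninferiority is declared in 95% of separated fits and 5% of the others.

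**6. Sensitivity analysis 5.** Expected events: 126 x 0.0305 + 63 x 0.0085 = 4.4. The protocol allows "Up to 22 study centers located in the European Union". If all 22 enrol, some will have no event and that fit is separated as well.

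**The case against.** The two readings exclude each other, and the large type I figures belong only to (b). The SAP's reference to maximum-likelihood estimates, its stated aim of greater stability, and the protocol's link between non-convergence and sparse strata all point toward (a). Under (a), a zero-event arm at step 4 looks benign: the fitted rate tends to zero, FM is defined on that table, and at 0/63 the step-4 fit matches FM on counts to six decimals. FM is also the only noninferiority test the SAP names, so the comparison with an exact test shows what an off-plan choice could do, not something the plan permits. The size of (b) depends on the scenario as well as the software: 11% vs 3% in both wound types gives 19-23%, and a model with only treatment and wound type gives 12-22% under homogeneous rates.

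Most of this stands as a limit on weight. The inflation is conditional, its lower end varies, and the exact-test example is illustrative. The benign reading of step 4 does not rescue the text, however. It requires accepting a separated fit, and a rule that accepts separated fits stops earlier, at a covariate-separated model. Getting the benign result needs one rule for covariates and another for treatment, and the SAP gives neither. The sensitivity analysis 5 point is minor, since that analysis does not drive the declaration.

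**Conclusion.** The concern holds. On the plan's own rates the undefined word governs most trials, and either reading leaves the single confirmatory test in trouble.

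- **Under (a):** no primary model is named in 59-62% of trials. This rests on the 0.85% Dermabond rate and falls to 20% at 2.5%.
- **Under (b):** the test does not control type I error. The main settings give 29-93%, and the mildest scenarios examined 12-23%, against about 5% on counts. The exact figure rests on assumed stopping rules, stratum sizes and the spread of events across strata, but it was well above nominal in every setting run.

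A zero-event arm alone does not distort FM; the inflation comes from covariate separation. This should be settled before anyone sees outcome data by arm.

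**What to change.** Amend SAP 13.1.1 with two sentences.

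1. A fit showing complete or quasi-complete separation counts as not converged; the same definition applies to sensitivity analysis 5.
2. If no model in steps 1-4 converges, or either arm has no events, the primary analysis is the FM test and 90% CI on the observed FAS counts. (The zero-event clause follows from the first sentence but is worth stating.)

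The terminal test equals step 4 whenever step 4 converges, and it is the test that reproduces the planned power. Simulated with both changes, type I error at 8.85% vs 0.85% is 4.9-6.0% (Monte Carlo SE about 0.35 points) and power is 85.8% with 28 lacerations or 88.5% with 40. The small excess over 5% comes from adjusted fits that are not separated, and the range is not general: at 13% vs 5% in both wound types the amended rule gives 6.6% (28 lacerations) and 6.3% (40), against 5.8% and 5.4% for FM on counts.

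No extra data or subjects are needed.
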